9.2. Informed Consent

The PI ([name]), or a suitably qualified deputy, will take informed consent from every participant involved in this study. This will be taken at their visit before any study specific procedures are performed.

Each participant must personally sign and date the latest approved version of the Informed Consent form at this visit. Written and verbal versions of the PIS and Informed Consent form (ICF) will be presented to the participants detailing no less than: the exact nature of the study; what it will involve for the participant; the implications and constraints of the protocol; and any risks involved in taking part. It will be clearly stated that the participant is free to withdraw from the study at any time for any reason, and with no obligation to give the reason for withdrawal. The participant will be allowed as much time as wished to consider the information, and the opportunity to question the Investigator, or other independent parties in order to decide whether they will participate in the study. Written Informed Consent will then be obtained by means of participant dated signature and dated signature of the person who presented and obtained the Informed Consent. A copy of the signed Informed Consent will be offered to the participant. The original signed form will be retained by the PI ([name]) at the study site

Visit 1 - Group 1 ('StR's):

Following enrolment for participation in this study, the StR's will be randomly allocated to receive either routine normal Deanery training (the 'control' group), or routine normal Deanery training plus additional simulation training (the 'intervention' group). Following randomisation all StR participants will undergo a baseline written and practical skills assessment within the OOSEC.

9.3. Subsequent Visits

Group 1a ('StR's') - Intervention group:

StR's randomised to the 'intervention group' will be required to complete the 4-week period of additional training outlined in section 9.3. Following completion of this additional training, participants within this group will undertake approximately 2 intra-operative assessments every 6 weeks over the duration of their 6-month clinical placements (total 8 assessments). The StR's will also undertake a final Technical Skills assessment in OOSEC Laboratory at 3 months into their placement (See Appendix A for Study Flow Diagram).

Group 1b ('StR's') – control group:

Participants within this group will undertake approximately 2 intra-operative assessments every 6 weeks over the duration of their 6-month clinical placements (total 8 assessments). The StR's will also undertake a final Technical Skills assessment in OOSEC Laboratory at 3 months into their placement (See Appendix A for Study Flow Diagram).

Group 2: 'Experts' and 'Fellows':

Following enrolment for participation in this study, all participants within this group will undergo a baseline practical skills assessment within the OOSEC. Participants within this group will then undertake a minimum of 5 separate intra-operative assessments each.

Patients:

Following enrolment for participation in this study, all patients will be asked to complete the pre-operative PROMs questionnaires (EQ-5D and OHS). These are part of routine clinical care, and are a mandatory for all patients undergoing THR in the NHS. The patients will not be asked to undertake any further assessments outside of their routine clinical care until the time of their scheduled post-operative out-patient department (OPD) clinic review appointment. All patients will only be followed up routinely following discharge by their named Consultant in an OPD clinic. This OPD appointment normally takes place 6 to 8 weeks following discharge. No additional clinic appointments or investigations will be required outside of the patients expected routine clinical care. At this visit the patients will be asked to complete the post-operative validated PROMs questionnaires (EQ-5D and OHS). This takes a few minutes and is the only extra outcome measure the patients are asked to complete.

9.4 Randomisation

Randomisation will be performed via a blinded sealed envelope containing information regarding which arm of the study they will participate in. As we only anticipate recruiting 2 StR's from each recruitment centre every 6 months, a more complex allocation/randomisation procedure will not be required. Over the 18 to 24-month study period we aim to recruit and randomise 6-8 StR's to the 'intervention' group, and randomise 6-8 StR's to the 'control' (routine training) group, with an even distribution of these StR's in both groups across the two recruiting hospital sites.

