7. STUDY DESIGN

Please see Appendix A for study flow diagram.

This is a prospective randomised controlled study designed to assess the impact of specific training interventions on surgical trainee's operative performance and patient outcomes following primary elective THR. We will also study the performance and patient outcomes of both 'Experts' and 'Fellows' in an additional comparator group, which will allow a potential expert standard in THR to be defined.

All study participants will be recruited from 2 Hospitals within the Thames Valley (Oxford) Post-graduate Medical Deanery, and will be composed of: Trauma & Orthopaedic Specialty Registrars ('StRs') holding national training numbers; Consultant Orthopaedic Surgeons ('Experts'); and Orthopaedic Arthroplasty Fellows ('Fellows'). Over the 18-24 month anticipated study period we aim on recruiting a total of up to 16 StR's, 8 Fellows, and 5 Experts. See section 9 for further details on participant recruitment.

StR's will be randomised in a 1:1 ratio to receive either: routine normal Deanery training (the control group, n=8); or routine normal Deanery training with additional simulation-based and cognitive learning (the intervention group, n=8). The intervention group will receive this training for 1-2 hours per week over a 4 to 6-week period. The 'Experts' and 'Fellows' will not be eligible for any intervention, and will act as a separate comparator group.

All participants will be assessed intra-operatively at set timepoints when performing elective primary THR surgery on patients within the named NHS Hospitals. The timepoints will vary depending upon each group. Each StR enrolled into this study will be assessed at a minimum of 8 separate THR operations over a 6-month period, commencing at 6 weeks in to their 6-month clinical placement. Both the 'Fellows' and 'Experts' will be assessed at a minimum of 5 separate THR operations depending upon the reliability of their performance data.

All patients in this study will have been listed for routine elective primary THR surgery under a named Orthopaedic Consultant on the NHS. There will be no interventions or deviations from routine clinical practise regarding the pre-operative investigations or work-up, the operation itself, the peri-operative care, or post-discharge follow-up.

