8. PARTICIPANT & PATIENT IDENTIFICATION

8.1. Consultants, Fellows, and Specialty Registrars

Group 1 ('StR's'): Trauma & Orthopaedic Specialty Registrars on Arthroplasty clinical placements.

Group 2 ('Experts' and 'Fellows'): Consultant Orthopaedic Surgeons, and nationally appointed Orthopaedic Arthroplasty Fellows.

Inclusion Criteria

Group 1 ('StR's'): All Specialty Registrars holding a National Training Numbers (NTN) in Trauma & Orthopaedic Surgery within the Thames Valley (Oxford) Deanery and who are or will be working on arthroplasty clinical placements at either the NOC, Oxford University Hospitals NHS Foundation Trust, or WGH, Buckinghamshire Healthcare NHS Trust over the specified recruitment period will be eligible for participation in this study. We anticipate recruiting 2 StR's from each recruitment centre every 6 months, over an 18 to 24-month period (total n = 12-16).

Group 2 ('Experts' and 'Fellows'): All Consultant Orthopaedic Surgeons with a sub-specialty practise in adult reconstructive (arthroplasty) surgery holding substantive posts at the NOC are eligible for participation in this study. The Consultant Orthopaedic Surgeons at WGH will not be required for the intra-operative assessment within this study, as we will gather sufficient motion data from the NOC Consultants to be able to benchmark an 'expert' performance. Nationally appointed Orthopaedic AF's working at either at either the NOC, Oxford University Hospitals NHS Foundation Trust, or WGH, Buckinghamshire Healthcare NHS Trust over the specified recruitment period will be eligible for participation in this study. We anticipate recruiting 2 AF's every 6-months over an 18 to 24-month period (total n = 6-8)

Exclusion Criteria

- Inability to comply with study procedures or timetable

- Moving outside of the area, relinquishing their position, or National Training Number.

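### Section 9.4 aims for equal arms spread evenly over the two hospitals but describes no restriction that would deliver this, and the planned tests have no site term

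*Combined protocol and SAP*

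**What the plan says.** Section 7 states that "StR's will be randomised in a 1:1 ratio", with 8 in each arm. Section 8.1 gives the recruitment rate: "We anticipate recruiting 2 StR's from each recruitment centre every 6 months, over an 18 to 24-month period (total n = 12-16"). Section 9.4 says that "we aim to recruit and randomise 6-8 StR's to the 'intervention' group", gives the same range for control, and adds "with an even distribution of these StR's in both groups across the two recruiting hospital sites".

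The method in Section 9.4 is a sealed envelope holding the arm. The reason for going no further is "As we only anticipate recruiting 2 StR's from each recruitment centre every 6 months", from which the section concludes that "a more complex allocation/randomisation procedure will not be required". Neither this section nor any other says how the sequence is generated, how many envelopes of each arm are prepared, whether they are held by site or in pairs, or who prepares them.

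Two other sections bear on the point. Section 9.2 has the PI or a deputy take consent, and places the StRs' baseline assessment after randomisation. Section 11 compares control and intervention StRs with Mann-Whitney, t and Chi-squared (or Fisher's exact) tests, none of which includes site.

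**The concern.** The plan states a result, equal arms evenly spread over two hospitals, without a procedure that produces it. The reason given, small numbers, points the other way: chance imbalance between arms is largest when few people are randomised.

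Site could matter here. The two hospitals belong to different NHS Trusts (Section 8.1). Under Section 9.7 the supervising Consultant confirms which cases the StR performs, may take over, and joins in completing the performance ratings. It is a reasonable inference, though not shown in the documents, that supervision and ratings differ between hospitals. If site and arm were associated by chance, the unadjusted tests in Section 11 would attribute part of that difference to the training.

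**Working it through.** **Inputs.** Two sites; 2 StRs per site every six months; 18 to 24 months, that is 3 to 4 intakes (Sections 8.1 and 9.4); 1:1 allocation (Section 7). The sequence method is not given, so three methods compatible with an envelope are compared. All figures assume that recruitment fills as planned.

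**The plan's own figure.** 2 sites × 2 StRs × 3 intakes = 12; 2 × 2 × 4 = 16. This reproduces 12-16 in total and 6-8 per arm. The documents state no probability of balance.

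**Method A: simple allocation (independent 50:50).**
- Equal arms overall: C(16,8)/2^16 = 12870/65536 = 19.6%; C(12,6)/2^12 = 924/4096 = 22.6%.
- Exact balance at both sites: (C(8,4)/2^8)² = (70/256)² = 7.5% for 4:4 with 16 StRs; (C(6,3)/2^6)² = (20/64)² = 9.8% for 3:3 with 12.
- Looser target, intervention count within one of half at each site: ((56+70+56)/256)² = 50.5%; ((15+20+15)/64)² = 61.0%.

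**Method B: fixed set with equal numbers per arm, not held by site.** Overall 1:1 is certain. Exact balance at both sites: C(8,4)²/C(16,8) = 4900/12870 = 38.1%; C(6,3)²/C(12,6) = 400/924 = 43.3%.

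**Method C: one envelope of each arm per pair of StRs at a site.** Balance is certain at both sites, 4:4 or 3:3.

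| Method | Exact balance at both sites, 16 StRs | 12 StRs |
|---|---|---|
| A: simple | 7.5% | 9.8% |
| B: fixed set, not by site | 38.1% | 43.3% |
| C: pair per site and intake | 100% | 100% |

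**What an imbalance does.** What enters an unadjusted difference in means is the site difference multiplied by the gap between arms in the share of StRs at one site. Splits are intervention:control, first site then second.
- 6:2 and 6:2: 6/12 − 2/4 = 0, no confounding.
- 6:2 and 4:4: 6/10 − 2/6 = 0.27 of the site difference.
- 6:2 and 2:6: 6/8 − 2/8 = 0.50 of the site difference.

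**What adjustment for site would cost.** The information on the arm effect is the sum over sites of n1·n0/n. For 4:4 and 4:4 it is 2 + 2 = 4.0. For 6:2 and 4:4 it is 1.5 + 2 = 3.5, so the variance rises by 4.0/3.5 − 1 = 14%. For 6:2 at each site, in either direction, it is 3.0, a rise of 33%.

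**Choice of block size.** A block of 6 per site, filled by three pairs, has C(6,3) = 20 sequences. The last pair has the same arm twice in 4 + 4 = 8 of them (40%). Anyone who knows the block size and the first four allocations then knows both remaining ones before consent, even if the pair is opened together. A block of 2 opened together does not have this weakness.

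**The case against.** A reader might infer that Section 9.4 rejects stratification and blocking, and so contradicts its own aim. The text does not support that. It names neither technique and only declines something more complex. The reason it gives, two StRs per centre per intake, fits one envelope of each arm per pair, which is already a site-stratified block of 2 and would explain why an even spread is expected.

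A reader might also take 7.5% as the plan's actual chance of balance. It is not: simple allocation is an assumption, the figure needs all 16 StRs and exact 4:4 at both sites, and Section 9.4 words the balance as an aim.

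Nor does imbalance at a site prove confounding, as the 6:2 and 6:2 case shows. Adjusting for site after an imbalance would have a moderate cost, 14% to 33% more variance in the examples. Section 8.2 limits differences in case mix by admitting only primary osteoarthritis and excluding complex pathology and previous surgery on the hip.

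All of this stands, and it limits the claim. It does not remove it. Methods A and B often miss the aim. Method C meets it, but opening the first envelope reveals the second allocation, and the plan does not require both StRs to have consented first. Section 9.7, which has the PI not disclose the arm in theatre, implies that the PI knows it, and the PI may also take consent. A restriction and a concealment rule therefore need to be written down whichever method was intended.

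**Conclusion.** The point holds as a cheap improvement, not as a demonstrated contradiction. The plan aims for 1:1 arms and an even spread over two hospitals, describes no restriction that would give them, and plans a control-versus-intervention comparison without site. The chance of exact balance at both sites runs from 7.5% (simple, 16 StRs) or 9.8% (simple, 12 StRs), through 38% to 43% (fixed set not held by site), to 100% (pair per site and intake). The documents do not say which applies.

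The consequence for the training comparison depends on two things the documents do not give: the size of any difference between hospitals, and the association between site and arm that happens to arise.

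**What to change.** - **Section 9.4.** Replace the sentence that declines a more complex procedure. State that randomisation is restricted within site and six-month rotation, with one intervention and one control envelope per pair of StRs at a site (block of 2). The envelopes are opaque, sequentially numbered and prepared by someone who does not enrol. Both are opened together, only after both StRs have consented. State in advance what happens if only one StR is recruited at a site in a rotation.
- **Section 9.2.** Have the baseline assessment completed before the envelopes are opened. This reverses the present order and should be declared as a change. It also means that unblinded StRs are not tested at baseline knowing their arm.
- **Section 11.** Account for site in the control-versus-intervention comparison, for example with a site-stratified rank test (van Elteren) in place of the plain Mann-Whitney test.

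**Cost.** List preparation by an independent person, and amendments to three sections. The first StR's allocation has to wait for the second. If a pair is not opened together, the second allocation is fully predictable, so the joint opening is essential. Balance is exact only where pairs fill.

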9.5 Blinding and code-breaking

Standard surgical practise will be followed. Patients are not formally blinded to which Surgeon (Consultant, Fellow, or StR) performs their operation, and are informed if requested. In line with standard surgical practise and training within the NHS, patients will provide informed consent that they understand no guarantees can be given that a particular person will perform the procedure. The person will, however, have appropriate experience.

Due to the nature of this study the StR's cannot be blinded to their allocations into either the 'control' or 'intervention' groups, however the assessment methods and any assessors will be blinded.

9.6 Description of study intervention(s),

The intervention to be tested is the simulation-based and cognitive learning package, which will be delivered to a randomised sub-group of 50% of the StR's recruited into this study. This will be delivered in a supervised setting within the OOSEC over a 4-week period for between 1 to 2 hours per week, over 3 to 4 consecutive but separate six-month placements (please see Appendix A for Study Flow Diagram). This will take place on a Wednesday afternoon, which is when all the Regional StR's are due to attend teaching in Oxford at the NOC.

The OOSEC is a secure enclosed laboratory space within the NOC, which contains all the necessary equipment required to run the simulation-based and cognitive learning training. The simulation training in general may include:

- 1) Focussed workshops on saw-bone models (simulated bones)
- 2) Digital and computer-based cognitive learning packages
- 3) Virtual reality platforms.

All participants within group 1 (StR's) will be asked to attend and complete baseline and final assessments within the OOSEC, which will consist of a multiple-choice questionnaire (MCQ) and a simulated procedure. Participants within group 2 (Consultants and Fellows) will only be required to complete a baseline simulated procedure.

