The outcome measures will be surgeon-specific and patient-specific. These outcome measures for the 'Trainee' group will commence following completion of the simulation training (if applicable), whereas they can commence immediately following study approval for the 'Expert' group. The surgeon-specific outcome measures will be the objective motion-analysis metrics generated by validated and extensively used wireless sensors placed on the elbows of surgeons under their sterile gowns during the operation; and subjective assessments of surgical trainee performance using validated and reliable forms of structured human grading. Patient-specific outcome measures will be collected for a pre-determined number of patients who have undergone a primary elective THR by any of the surgeon participants in this study. All patient-specific outcome measures (with the exception of a post-operative questionnaire) are routinely collected as part of the patients NHS clinical care, and no other additional investigations are required for conducting this research. All patients will be asked to provide their written informed consent for the use of their data in this study. The patient-specific outcome measures include: pre- and post-operative blood tests and radiograph (X-ray) analysis; the incidence of blood transfusions and any other peri-operative complications; the in-patient length of stay; and two patient-reported outcome measure (PROMs) questionnaires.

Statistical analysis will then be performed on the data collected, specifically aiming to identify any significant differences in either surgeon performance metrics, or patient outcome measures between:

- 1) The StR's who have undertaken additional simulation training versus those who have routine Deanery training.
- 2) The 'Trainee' group and the 'Expert' group. A sub-group analysis may be performed within the 'Expert' group also to determine any differences between the Consultants and Fellows.

In summary, this novel research will use validated methodology and routinely collected patient outcome measures in order to determine the impact of simulation training on surgical trainee performance and patient outcomes following a primary elective THR, and also help to benchmark an expert level of performance in this commonly performed and highly effective operation. The results of this study will hopefully help in shaping the future of orthopaedic surgical training and assessment within the United Kingdom.

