6. OBJECTIVES AND OUTCOME MEASURES

Objectives	Outcome Measures	Timepoints of evaluation
Primary To assess the impact of simulation training on surgical trainee performance and patient outcomes following THR.	Participants: 
 Wireless motion data metrics from elbow worn sensors (hand movements, path length and time taken) Global Rating Scales (GRS). Objective Structured Assessment of Technical Skills (OSATS). Surgical checklists. Patients: 
 X-ray analysis of THR.[4] Blood loss and transfusion rates. Peri-operative patient morbidity In-patient length of stay. PROMs: EQ-5D and OHS. 	Intra-operative assessments to be performed at a minimum of 8 separate THR operations for each participant in Group 1 (StR'S) over a 6-month period. Outcome measures data will be collected for all patients who have had a THR performed by any participant as the lead surgeon in this study.
Secondary To define an expert standard when performing a primary elective THR. To determine if operative surgeon performance metrics during a THR relate to surgical experience, or patient outcomes.	Participants: 
 Wireless motion data metrics from elbow worn sensors (hand movements, path length and time taken) Patients: 
 X-ray analysis of THR.[4] Blood loss and transfusion rates. Peri-operative patient morbidity In-patient length of stay. PROMs: EQ-5D and OHS. 	Intra-operative assessments at a minimum of 5 separate THR operations for each participant in Group 2 (Experts & Fellows). Outcome measures data will be collected for all patients who have had a THR performed by any participant as the lead surgeon.

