9.7 Intra-operative surgeon performance data collection

The following protocol will apply to all episodes of intra-operative performance data collection for StR's and Fellows. The intra-operative data collection for Consultant performed operations will differ slightly in that they require no supervision, and no surgeon will 'take over' the operation. However, the methods for recording the intra-operative data will remain the same.

A maximum of two study participants (excluding Consultants) will attend any given list. The PI ([name]) will attend the World Health Organisation (WHO) briefing in theatre on the morning of the list, introduce themselves and explain their role during the list. If recording an StR, neither the participant or PI will disclose which arm of the study the participants are in (routine training, or additional simulation training). The supervising Consultant will confirm the cases on the list the StR or AF's will be performing under supervision and training.

Operative protocol

After anaesthesia and patient set-up, the supervising Consultant and participant will scrub in up in the usual manner with the motion sensors in position on the lead surgeon's elbows under their sterile gown (see Appendix C). The procedure will then continue routinely and normally, but with the PI collecting motion data via the wireless Bluetooth sensors. The PI will also manually record the timings of each stage of the THR operation. This process will allow synchronisation of motion data to the participants progression throughout the stages of the operation. Data collection will stop when the dressing has been applied to the surgical wound.

Following completion of the operation, the participants in conjunction with the supervising Consultant will be asked to complete short written assessments of the lead surgeons' intra-operative performance. These assessments may include: Global Rating Scales (GRS), Objective Structured Assessment of Technical Skills (OSATS), and surgical checklists.

Intra-operative deviations or interruptions

Sometimes the supervising Consultant needs to take over part or all of an operation if it proves particularly difficult. In the event that a procedure has to be taken over completely by the Consultant then data recording will stop. If minor adjustments only are made by the Consultant during the operation then these will be noted and time marked against the motion data.

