12 DATA MANAGEMENT

Within this study both patients and participants will have all of their personal data anonymised via the use of Unique Patient or Participant Identifiers (UPI's). A master list of key linking identifiers for both patients

and participants will be kept on a password protected file on the OUH secure Trust Network Server. Only completely anonymised data will be used outside of OUH Trust property, which will be kept on a password-protected University owned laptop or hard-drive. We plan on keeping study data for a period of 5 years following completion on the study (up to December 2026), before securely disposing of it. We believe that this storage is appropriate as the core content is scientific research data and is therefore in the public interest. Furthermore, we will require access to this data in the case of individuals wishing to scrutinise the scientific methodology, results, or conclusions of our study.

Intra-Operative Data

Raw data will be produced from the wireless sensors. Please see section 12.3 for further details regarding the recording, transfer, and storage of this data.

Other 'personal data'

1) Electronic Patient Record Data

The following data will be obtained from the NHS Electronic Patient Records (EPR), which includes the Insignia Picture Archiving and Communication System (PACS), and the Theatre Management System (TMS):

- X-ray (radiograph) analysis.
- Theatre time usage.
- Blood test & transfusion rate analysis.
- Peri-operative morbidity (30 day).
- In-patient length of stay.
- Patient demographics (age, gender, BMI)

2) Questionnaire Data

Patient Questionnaire Data

The patient questionnaires consist of the following components:

- Patient Reported Outcome Measures: The OHS and EQ-5D.

Participant (Medical Health Professionals) Questionnaire Data

Written assessments of intra-operative performance will be conducted shortly after completion of a recorded THR. These assessments may include: Global Rating Scales (GRS), Objective Structured Assessment of Technical Skills (OSATS), and surgical checklists. The data collected from these will be anonymised as it will be linked with the UPI, and not provide any names or other personal information. The hard copies will be transcribed into digital format as soon as possible, which will be stored onto a password protected encrypted file on a University owned computer/hard-drive. The hard copies of the forms will then be disposed of.

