16.10 Expenses and Benefits

No additional expenses will be made for either the patient's or participants involvement in this study.

The direct benefits to participants may include:

- The opportunity to practice and develop their surgical skills under supervision in the simulation laboratory.
- The opportunity to objectively assess their surgical skills using the wireless motion sensors, which may in turn highlight areas for improvement.
- The opportunity to complete work-based assessments as part of the study (for example the PBA form), which are currently an integral part of surgical training requirements.

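### Assessors are declared blinded, but unblinded trainees help score their own operations on the GRS, OSATS and checklists, and the plan does not say whose score is analysed

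*Combined protocol and SAP*

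**What the plan says.** Section 9.5 (Blinding and code-breaking) states that the StRs "cannot be blinded to their allocations" but that "the assessment methods and any assessors will be blinded". It lists no exception.

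Section 9.7 (Operative protocol) describes who fills in the forms after each operation: "the participants in conjunction with the supervising Consultant will be asked to complete short written assessments of the lead surgeons' intra-operative performance". The tools that may be used are the GRS, OSATS and surgical checklists. Section 9.7 also sets a rule for recorded StR lists that "neither the participant or PI will disclose which arm of the study the participants are in".

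In section 6 all three tools are outcome measures for the primary objective: "To assess the impact of simulation training on surgical trainee performance and patient outcomes following THR". Section 2 describes them as "subjective assessments of surgical trainee performance using validated and reliable forms of structured human grading" and names no rater. Section 12 says only this about timing: "Written assessments of intra-operative performance will be conducted shortly after completion of a recorded THR". It then covers anonymisation and storage, again without naming the rater.

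**The concern.** In an StR case the participant is the lead surgeon, so section 9.7 gives a person who knows the allocation a part in rating their own operation. That cannot be squared with a statement that every assessor is blinded.

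Masking matters most for ratings like these, because they depend on judgement and the rater has an interest in the result. If a joint score or the trainee's own score is analysed, a difference between arms may partly reflect the trainee's knowledge of having had, or not had, the extra training. If a separate Consultant score is analysed, the trainee's direct input is gone. The plan allows either, so the choice could be made after the scores are known.

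A smaller, related point concerns the radiographs. Section 11 masks the two Consultant film graders to patient and surgeon. It gives no such provision for the PI, who alone reads cup inclination and version, so only the general sentence in section 9.5 covers those readings.

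**Working it through.** There is no stated figure to reproduce. The check is a comparison of the text, followed by simple counts.

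**1. The two sections side by side.**
- Section 9.5: trainees know their arm; all assessors are blinded.
- Section 9.7: the trainee and the Consultant together complete the assessments of the lead surgeon.
- Section 8.2 requires the operation to be led by a surgeon participant, so in StR cases the person rated is the trainee who helps to complete the form.

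The wording of 9.7 fits either one agreed form or two separate forms. Under both, the trainee is an unblinded rater. Only with two forms does a Consultant score exist that is free of the trainee's input.

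**2. Does any other section settle whose score counts?**

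| Section | What it gives | Rater or analysed score named? |
|---|---|---|
| 2 | Type of grading | No |
| 6 | Tools listed under the primary objective | No |
| 11 | Tests for motion data, radiographs and other listed outcomes; GRS, OSATS and checklists not mentioned | No |
| 12 | Timing, anonymisation and storage of the forms | No |
| 12.4 | Forms listed as source data | No |
| 16.10 | Benefit to participants: "The opportunity to complete work-based assessments as part of the study" | No |

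Section 16.10 makes a feedback role for the trainee plausible. Its example is the PBA form, which is not one of the tools in section 9.7, so it does not settle who scores the GRS or OSATS.

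**3. Is the Consultant masked?** The non-disclosure rule in section 9.7 is the stated mechanism. A separate Consultant score could therefore still be masked.

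**4. How much is affected.**
- Surgeon outcomes in section 6: motion metrics, GRS, OSATS, checklists = 4, of which 3 are ratings. Adding the five patient outcomes gives 3 of 9.
- StR operations with 16 StRs (section 3): 16 × 8 = 128, or 8 × 8 = 64 per arm.
- StR operations with 12 StRs (lower end of section 8.1): 12 × 8 = 96, or 6 × 8 = 48 per arm.

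These are upper counts at the planned eight operations per StR. The tools are optional as worded, and recording stops if the Consultant takes over completely.

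**5. Illustration of size (assumed values, not from the documents).** Let *d* be the between-arm shift in self-rating caused by knowing the arm, and *w* the trainee's weight in the analysed score. The shift in the arm difference is *w* × *d*. Take *d* = 0.2 to 0.5 SD.

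| Score analysed | *w* | Shift in arm difference |
|---|---|---|
| Separate Consultant score | 0 | 0 |
| Joint score, equal weights | 0.5 | 0.5 × 0.2 = 0.10 to 0.5 × 0.5 = 0.25 SD |
| Trainee's own score | 1 | 0.20 to 0.50 SD |

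**6. Cup angles.** Section 9.7 has the PI in theatre collecting the motion data, and a rule that the PI must not disclose the arm suggests that the PI knows it. This is an inference. Films to be read: 128 + 40 + 25 = 193 (section 3), of which 128 belong to StR patients.

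**The case against.** The best defence is that section 9.5 separates two classes of people: the StRs, who cannot be masked, and the assessors, meaning everyone else. Section 2 treats trainees as the people being graded, and the non-disclosure rule protects the external rater. On that reading section 9.5 is not false and only the rater's role in 9.7 is unclear. This softens the contradiction but does not remove the problem, because 9.7 followed as written still puts an unblinded self-rater's input into an outcome compared between arms.

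Several other points are fair and limit the claim:
- The harm is conditional. It disappears if a separate Consultant score is used, and no section says a trainee-only score would be analysed, so the largest figures belong to the least supported case.
- The SD range is assumed and says nothing about the true bias in this trial.
- Section 2 calls the tools validated, reliable and structured as well as subjective. Structure may reduce the effect of expectation; it does not blind the rater.
- The ratings are three of nine primary-objective outcomes, and the motion metrics do not depend on them.
- The absence of these scales from section 11 is in itself an analysis-plan gap. It matters here only because it leaves the choice of rater open.
- The cup-angle risk is smaller. A published measurement method is cited, section 11 gives no target range that would make one direction favourable, and the PI's knowledge of the arm is inferred.

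**Conclusion.** The concern holds. The blanket blinding statement is not true of the trainee as rater under section 9.7, and no section says whose score is compared. Blinding is therefore not secured for three of the four surgeon outcomes under the primary objective, across up to 128 StR operations (96 with 12 StRs).

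Confidence is high on the inconsistency and the missing rater rule. The size of any bias is unknown: on the assumed values the shift runs from 0 to 0.50 SD, depending on which score is used. This should be corrected, but it does not invalidate the trial. The motion metrics and the patient outcomes do not rest on these ratings, and a masked Consultant score remains possible. The cup-angle point is secondary.

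**What to change.** **Main change.**
- In section 9.7, have the supervising Consultant score the GRS, OSATS and checklists independently, on a separate form, before any discussion with the trainee. Record the rater as a data field.
- In section 11, name the Consultant's score as the one compared between arms. Keep trainee self-scores as descriptive data.
- In section 9.5, limit the blinding claim to the assessors who are actually masked, say how each is masked, and state that the Consultant's masking rests on non-disclosure.

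**Secondary change.** Have inclination and version read on films coded by study identifier and put in random order, with patient, surgeon and arm hidden from the reader.

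**Cost.** The main change needs a revised form, wording changes in three sections and one data field, with no new assessor. The trainee no longer shares in the trial score, but feedback can follow the Consultant's scoring. The film change needs a team member other than the PI to code and order about 193 films, or 128 if limited to StR patients. Section 12.5 refers to research team members who might do this.

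**What remains.** The Consultant's own masking is no stronger than before. Training runs at the NOC, a study hospital, on the regional teaching afternoon (section 9.6). All StRs are due there that day, so attendance alone does not reveal the arm, but it could still become known.
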